10 DATA SAFETY MONITORING

10.1 Data and Safety Monitoring Committee

A DSMC will be established by the study team in cooperation with the sponsor to assess at intervals the progress of a clinical trial, safety data, and critical efficacy variables and recommend to the sponsor whether to continue, modify or terminate the trial. The DSMC will operate according to guidelines documented in a DSMC charter. Minutes will be taken to provide a written record of the DSMC meetings, including interim results; these will be available for review when the trial is complete. The DSMC will be a separate entity from the Institutional Review Board (IRB). The independence of the DSMC is intended to control the sharing of important comparative information and to protect the integrity of the clinical trial from adverse impact resulting from access to trial information. DSMC members will be external to Stanford University, will not participate in the study as investigators, and will not have conflicts of interest regarding the study or the investigational product. The composition of the DSMC will include at minimum:

- DSMC Chair, having experience and expertise in clinical trials
- Scientist with expertise in viral infectious diseases.
- Biostatistician with expertise in clinical trials.

Confidential Page 33 of 42

The DSMC will meet before the study and during an interim analysis to review progress of the clinical trial and safety data. A formal interim analysis for overwhelming efficacy is planned for the interim analysis. There are no plans to stop for futility. the DSMC may choose to stop enrollment on the basis of safety data observed. If safety concerns are found, further enrollment will not be allowed until issues are resolved. Any recommendation by the DSMC to stop the trial early will be based on a balanced review of safety and efficacy data and a consideration of whether an adequate amount of information is available to reach a conclusive decision.

The study PI will distribute study information to the DSMC prior to a scheduled meeting. The DSMC may request additions and other modifications to this information on a one-time or continuing basis. This information will consist of two parts: (1) information on study progress such as accrual, baseline characteristics, and other general information on study status and (2) any confidential data on study outcomes, including safety data. A formal report from the DSMC should be supplied to the PI within 3 days of each meeting. Each report should conclude with a recommendation to continue or to terminate the study. This recommendation should be made by formal majority vote. A recommendation to terminate the study should be transmitted to the PI and IRBs as rapidly as possible, by immediate telephone and fax if sufficiently urgent. In the event of a split vote in favor of continuation, a minority report should be contained within the regular DSMC report.

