3 DESIGN

This is a Phase 2 double blinded and placebo controlled randomized trial evaluating the efficacy and safety of camostat mesilate in adult subjects with PCR-positive, mild-moderate or COVID-19 infections.

Subjects will be randomized to receive either camostat mesilate + current Standard of Care (SOC) or SOC + placebo.

Study participants will be randomly assigned 1:1 to two tablets of oral camostat mesilate (200 mg) four times a day or current standard of care for 10 days.

Subjects in the SOC arm will receive a placebo. The total anticipated duration of the study for each patient is 28 days.

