8.3.3 Evaluating and Reporting of Adverse Events

All AEs (i.e. a new event or an exacerbation of a pre-existing condition) that occur after dosing with camostat mesilate and after completion of baseline assessments in the SOC + placebo arm, must be recorded as an AE or SAE (if applicable), on the Adverse Event eCRF and SAE form, as applicable. The Investigator must follow all AEs until the AE resolves, or until the Investigator and/or the Medical Monitor determine the event is chronic or clinically stable. If an AE remains unresolved at the conclusion of the study, the Investigator and Medical Monitor will make a clinical assessment to determine whether continued follow-up of the AE is warranted. All subjects who have received at least one exposure to study therapy will be evaluated for safety of study treatment.

The Investigator should attempt to establish a diagnosis of the event based on signs, symptoms and/or other clinical information. In such cases, the diagnosis should be documented as the AE and not the individual signs/symptoms.

All AEs must be promptly documented on the Adverse Event eCRF and assessed by the Investigator. Details of the event must include the dates of onset and resolution, severity, relationship to study drug, seriousness, and whether the event caused the subject to withdraw from the study, outcome and timing with regard to administration of the study drug. We will categorize the AES using the Division of AIDS Table for Grading the Severity of Adult and Pediatric Adverse Events.

Severity: Severity should be graded and recorded as follows:

- Grade 1 Mild: No or minimal interference with usual activities; intervention not indicated
- Grade 2 Moderate: Greater than minimal interference with usual activity; intervention indicated
- Grade 3 Severe: Inability to carry out usual activity, incapacitating; requires intervention or hospitalization
- Grade 4 Potentially life-threatening: Inability to perform self-care; intervention indicated to prevent permanent impairment, disability or death
- Grade 5 Death

Relationship: The relationship of the Adverse Event to the study drug will be determined by the Principal Investigator, and assessed using the following definitions:

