9.10 Safety Analysis

Confidential Page 32 of 42

The frequency of adverse events and serious adverse events will be tabulated by type and by treatment arm. AEs will be compared by arm using the Chi-squared test or Fisher's exact test, as appropriate, in the safety analysis set.

The original exact terms in the electronic data capture (EDC) system used by Investigators to identify AEs other than symptoms of COVID-19 will be fully described and coded according to the Medical Dictionary for Regulatory Activities (MedDRA). Treatment-emergent AEs will be defined as those occurring coincident with start of treatment and through 28 days post-treatment. TEAEs will be summarized overall and by treatment group and by MedDRA body organ system and preferred term, severity, relatedness, and seriousness.

An overall summary of TEAEs will be presented by treatment, with subject counts and percentages of subjects with the event. This summary will include subjects with any TEAE, any treatment-related TEAE, any serious TEAE, any treatment-related serious TEAE, TEAEs leading to study infusion discontinuation, treatment-related TEAEs leading to study infusion discontinuation, TEAEs leading to death, and treatment-related TEAEs leading to death. The difference in proportions between treatment groups in each of these categories will be calculated.

Summaries of changes over time in laboratory parameters, as well as counts and percentages of laboratory parameters that are Low, Normal, and High compared to the reference ranges will be presented by treatment at each visit and time point. Shift tables will be presented for laboratory parameters with defined severity grades.

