10.2 Interim Analysis

An interim analysis for safety and overwhelming efficacy will be performed once 50% of patients have 24 hours of follow-up complete. The DSMC will meet within a week after 50% enrollment is reached to review the safety data collected within the first 24 hours of follow-up on all enrolled patients. We additionally expect blood count labs collected at day 5 to be available in approximately 25% of patients at the time of the DSMC review.

The DSMC will also review the efficacy data on all randomized participants at this meeting. The interim efficacy analysis will use the same methods as are planned for the final analysis using the ITT analysis. Based on the results of the interim analysis, the DSMC will either recommend to the sponsor to terminate the study for overwhelming efficacy (p<0.00001 at the interim analysis), terminate the study for safety concerns, modify the study, or continue the study as planned. No formal stopping rules for futility are planned.

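### Section 10.1 sends the confidential interim outcome data to the DSMC through the PI, who also judges AE relatedness, so the PI could see by-arm trends

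*Combined protocol and SAP*

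**What the plan says.** Section 3 sets the design: "This is a Phase 2 double blinded and placebo controlled randomized trial".

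Section 10.1 gives the purpose of an independent committee: "The independence of the DSMC is intended to control the sharing of important comparative information". It also holds back the DSMC minutes, which include interim results, until the trial is complete.

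The same section then describes what the committee receives: "The study PI will distribute study information to the DSMC prior to a scheduled meeting". That information has two parts. The first is accrual, baseline characteristics and general study status. The second is "any confidential data on study outcomes, including safety data". After each meeting a formal DSMC report goes to the PI within 3 days, and nothing is said about whether it may contain comparative results.

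On the interim, Section 10.2 says: "The interim efficacy analysis will use the same methods as are planned for the final analysis using the ITT analysis". The efficacy boundary is p<0.00001.

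Section 8.3.3 says: "The relationship of the Adverse Event to the study drug will be determined by the Principal Investigator".

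**The concern.** Section 10.1 names one carrier for both parts of the DSMC package, and that carrier is the PI of a double-blind trial. Sponsors usually split such a package so that blinded trial staff handle only pooled information. Here the text makes the split by content but not by route.

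If the PI learns how the arms are trending, several later judgements could be coloured by it:

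- the relatedness call on each adverse event;
- withdrawal of a subject at the investigator's discretion (Section 5.3);
- the decision that a candidate is ineligible for any reason (Section 5.2);
- decisions about how the trial is run.

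Relatedness has a direct analytical consequence, because Section 9.10 compares treatment-related TEAEs between the groups.

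**Working it through.** The plan gives no figure for this point, so the check sets the sections side by side and then sizes the period affected.

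**1. Does the routing cover the confidential part?** Yes. Section 10.1 makes the PI the distributor of the information and then defines it as both parts. No exception is stated for the second.

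**2. Is the confidential part comparative at the interim?** Section 10.1 does not say so. It follows from the analysis plan:

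- Section 10.2 requires the final-analysis methods at the interim.
- Section 9.8 defines the primary method as a regression of log(AUC) on treatment arm, site, age and sex. It cannot be run without arm codes, and its result is a between-arm contrast.
- Section 9.10 says of safety: "The frequency of adverse events and serious adverse events will be tabulated by type and by treatment arm". That is the general safety plan; the layout of the interim tables is not specified.

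A between-arm efficacy result must therefore exist for the DSMC meeting, and the only described route to the DSMC is the PI.

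**3. Is there a safeguard elsewhere in the text?** None was found. No section names an unblinded or independent statistician, provides a sealed or closed report, or limits by-arm content in the report returned to the PI. Section 10.1 refers to a DSMC charter, whose contents are not given.

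**4. How much of the trial follows the interim?**

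- Participants: Section 9.2 plans 120, and Section 10.2 triggers the interim when 50% have 24 hours of follow-up. 0.5 × 120 = 60, which leaves about 120 − 60 = 60 to enrol. No accrual rate is given. If enrolment continues up to the meeting, the number left is somewhat smaller.
- Follow-up: Section 10.2 expects Day 5 blood counts in about 25% of patients at the review, without stating the base. If the base is the 60 enrolled, 0.25 × 60 = 15. If it is all 120, 0.25 × 120 = 30. Assume that lab availability tracks visits. Anyone past Day 10 is also past Day 5, so at most 15 to 30 Day 10 visits precede the review. At least 120 − 30 = 90 to 120 − 15 = 105 of 120 follow it, or 75% to 87.5%. The share for Day 28 visits is at least as large.

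**5. Which outcomes can be affected?**

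| Outcome | Source | Exposure to knowledge of trends |
|---|---|---|
| Primary AUC through Day 10 | RT-PCR on self-collected nasal swabs (Section 8.1) | Low |
| Symptom resolution | Participant's daily questionnaire (Section 9.9) | Low |
| 7-point clinical status | Hospitalisation, oxygen or ventilation use, death (Section 7.3) | Low |
| AE relatedness | PI's judgement (Section 8.3.3) | Direct |
| Discretionary withdrawal, enrolment, conduct | Investigator or PI decisions (Sections 5.2, 5.3) | Direct |

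**The case against.** The strongest reply is that distributing a package need not mean preparing or reading it. The PI could forward a closed report unopened, which would fit both the routing sentence and the stated purpose of independence. Routing is also a natural subject for the charter, which may already settle it. This stands as a limit on certainty: the documents do not show that the PI sees by-arm data. It does not remove the point, because the protocol assigns the task to the PI without qualification. A charter that says otherwise would leave the two documents in conflict.

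The second reply concerns harm, and most of it stands. The DSMC reviews safety from the first 24 hours of follow-up, and few participants could have swabs through Day 10, so there is little efficacy trend to leak. The primary endpoint and the clinical status scale leave little room for assessor bias. Section 7.1 allows a designee to perform the Day 1 examination, so the PI is not necessarily the examiner.

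A reader might infer that the PI would learn individual treatment assignments. The documents do not support that. Results aggregated by arm do not identify any participant's arm, and no section describes arm-coded listings passing through the PI. A reader might also infer that the primary result is compromised. The laboratory endpoint and the sparse interim efficacy data argue against it.

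**Conclusion.** The point holds as a fault in routing. Followed as written, Section 10.1 puts the confidential interim data in the hands of the person who determines AE relatedness, against the purpose stated in the same section.

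The exposure is knowledge of interim trends. It could affect relatedness, discretionary withdrawal, enrolment and trial conduct for roughly 60 of 120 participants still to be enrolled, and for the remaining follow-up of those already in. It does not reveal individual assignments, and the primary endpoint is largely protected. The wording should be corrected before the interim, but it does not threaten the main efficacy conclusion.

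This rests on three assumptions: that the second part of the package carries the by-arm interim output, that a person who distributes the package is able to read it, and that the charter does not already send it another way.

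**What to change.** Amend Section 10.1, and the charter if it does not already say so:

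- The PI supplies only the first part (accrual, baseline characteristics and study status), pooled across arms.
- The second part is prepared by a statistician outside blinded trial conduct, or by the DSMC biostatistician from the data export and the randomization list, and goes directly to the DSMC.
- The DSMC report to the PI carries the recommendation, any minority report and any safety information needed to act, but no by-arm results. A bare recommendation would not be enough. Section 10.1 requires a minority report after a split vote for continuation, and the DSMC may recommend modification or stop enrolment until safety issues are resolved.

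Endpoints, sample size and alpha are untouched. The cost is a wording change plus one added task: an existing statistician outside blinded conduct, or the DSMC biostatistician already required by Section 10.1, takes on the closed report. The documents name no trial statistician, so the sponsor must confirm who is available.

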10.2 Interim Analysis

An interim analysis for safety and overwhelming efficacy will be performed once 50% of patients have 24 hours of follow-up complete. The DSMC will meet within a week after 50% enrollment is reached to review the safety data collected within the first 24 hours of follow-up on all enrolled patients. We additionally expect blood count labs collected at day 5 to be available in approximately 25% of patients at the time of the DSMC review.

The DSMC will also review the efficacy data on all randomized participants at this meeting. The interim efficacy analysis will use the same methods as are planned for the final analysis using the ITT analysis. Based on the results of the interim analysis, the DSMC will either recommend to the sponsor to terminate the study for overwhelming efficacy (p<0.00001 at the interim analysis), terminate the study for safety concerns, modify the study, or continue the study as planned. No formal stopping rules for futility are planned.

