1 SYNOPSIS

| Title | A Phase 2 Randomized, Double Blinded, Placebo Controlled Study of Oral Camostat Mesilate Compared to Standard Supportive Care in Subjects with Mild-Moderate COVID-19 | | | | | |
|------------|---|--|--|--|--|--|
| Design | This is a Phase 2 Double Blinded, Placebo Controlled Study evaluating the efficacy and safety of oral camostat mesilate in adult subjects with PCR-positive, mild-moderate COVID-19 infections. | | | | | |
| | Subjects will be randomized to receive either camostat mesilate +current Standard of Care (SOC) or SOC + placebo. | | | | | |
| | Study participants will be randomly assigned 1:1 to two tablets of oral camostat mesilate (100 mg/tablet) four times a day plus SOC or SOC plus placebo for 10 days. | | | | | |
| | Subjects in the SOC arm will receive placebo. | | | | | |
| | The total anticipated duration of the study for each patient is 28 days. | | | | | |
| Objectives | Primary Objective To evaluate the efficacy of oral Foipan (camostat mesilate, 200 mg, four times a day for ten days) compared with placebo plus current standard of care in reducing the area under the curve (AUC) through day 10 of viral shedding of SARS-CoV-2 virus in patients with mild-moderate COVID-19. Secondary Objectives 1. To evaluate the efficacy of oral camostat mesilate plus SOC compared with placebo plus current SOC in reducing the AUC up through day 28 of viral shedding of SARS-CoV-2 virus in patients with mild-moderate COVID-19. 2. To evaluate the efficacy of oral camostat mesilate plus SOC compared with placebo plus current SOC in reducing the duration of viral shedding of SARS-CoV-2 virus in patients with mild-moderate COVID-19. 3. To evaluate the efficacy of oral camostat mesilate plus SOC compared with placebo plus SOC in reducing the duration of symptoms, hospitalizations or ED visits, or mortality in patients with mild-moderate COVID-19. 4. To evaluate the proportion of individuals with a negative SARS-CoV2 RT PCR test on days 7, 14 and 28. 5. To assess the safety and tolerability of camostat mesilate in this subject population. 6. To assess the development of antibodies against SARS-CoV-2 7. To determine drug levels at one time point on day 5 using the current dosing scheme. | | | | | |
| Endpoints | Primary Endpoint: | | | | | |

Confidential Page 6 of 42

| | AUC of shedding of SARS-CoV-2 virus calculated using the RT-PCR measures of viral load from self-collected nasal swabs on days 1-10. | | | |

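### The interim efficacy stopping test is triggered at 24 hours of follow-up, but its endpoint is a Day 1-10 AUC that recent enrollees cannot yet have

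*Combined protocol and SAP*

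**What the plan says.** Section 10.2 sets the trigger: "An interim analysis for safety and overwhelming efficacy will be performed once 50% of patients have 24 hours of follow-up complete". The synopsis and 9.2 give the same trigger. On timing, 10.2 adds "The DSMC will meet within a week after 50% enrollment is reached", and on population, "The DSMC will also review the efficacy data on all randomized participants at this meeting". On method it says "The interim efficacy analysis will use the same methods as are planned for the final analysis using the ITT analysis". Stopping for efficacy requires p<0.00001. Section 10.1 confirms that the test is formal: "A formal interim analysis for overwhelming efficacy is planned for the interim analysis".

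The synopsis defines the primary endpoint as "AUC of shedding of SARS-CoV-2 virus calculated using the RT-PCR measures of viral load from self-collected nasal swabs on days 1-10". Section 9.1 states the null hypothesis for AUC through Day 10. Section 9.8 regresses log(AUC) on treatment arm, site, age and sex, and describes the AUC as taken over follow-up, without repeating the Day 10 limit.

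Section 9.4 places every efficacy analysis in the ITT population of all randomized patients. Section 9.9 applies multiple imputation under missing at random to any analysis with missing endpoint data. The predictors it lists are baseline characteristics, treatment assignment and reasons for missingness. Section 9 defers missing-data detail to a formal SAP, and 10.1 defers DSMC operation to a charter. Neither is among these documents.

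**The concern.** Day 10 falls nine days after Day 1. A trigger at 24 hours of follow-up therefore guarantees that the most recently randomized participants have no complete AUC, and 10.2 puts them in the test. Inclusion criterion 8 (5.1) has participants bring their self-collected swabs to the Day 5, 10 and 28 visits, so Day 6-10 swabs reach the site only at the Day 10 visit.

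No section says what the test does with these people. Section 10.2 names no interim endpoint, and 9.9 does not say whether a swab not yet due counts as missing and is imputed. At stake is a prespecified stopping test that may rest partly, or under fast accrual largely, on outcomes nobody has observed. Its ability to do its stated job falls as fewer AUCs are complete.

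**Working it through.** **The plan's own figures.** Section 9.2 splits alpha as 0.00001 (interim) + 0.04999 (final) = 0.05, which agrees with 9.1. It states 80% power for 60 per arm at a standardized effect d = 0.5. At two-sided alpha 0.04999 the normal approximation gives 78.2% and the noncentral t gives 77.5%. The stated 80% is thus only approximate, which is a separate matter.

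**Complete AUCs at the review.** Inputs from the documents: 120 planned, trigger at 60, review within 7 days of 50% enrolment, Day 10 = Day 1 + 9 days. Assumed, because accrual is not stated: uniform accrual of r per day and a data cut L days after the 60th enrolment.

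- Days to the 60th enrolment: T = 60/r
- Randomized at the cut: min(120, 60 + rL)
- Past Day 10: r(T + L − 9), not below 0

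| r per day | L = 1: complete / randomized | L = 7: complete / randomized |
|---|---|---|
| 0.5 | 56 / 60.5 | 59 / 63.5 |
| 1 | 52 / 61 | 58 / 67 |
| 3 | 36 / 63 | 54 / 81 |
| 5 | 20 / 65 | 50 / 95 |
| 10 | 0 / 70 | 40 / 120 |

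For example, at r = 3 and L = 1: T = 20, 3 × (20 + 1 − 9) = 36 complete, and 60 + 3 = 63 randomized. While enrolment continues, the number incomplete is 9r. At 0.5/day that is 4.5 of 60.5 to 63.5, about 7%; at 1/day it is 9 of 61 to 67, or 13% to 15%. The fractions shrink further with slower accrual but do not reach zero. These counts are upper limits, because missed swabs, dropout and assay time are ignored.

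No AUC is complete when T + L ≤ 9. This needs r ≥ 60/8 = 7.5/day with a 1-day review, or 60/6 = 10/day with a 3-day review.

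**Chance of crossing p<0.00001.** Two-sample noncentral t with n per arm, df = 2n − 2, noncentrality d√(n/2). These are complete-case figures, not the imputed ITT analysis.

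| Complete AUCs (per arm) | Observed d needed | d = 0.5 | d = 1.0 | d = 1.5 |
|---|---|---|---|---|
| 60 (30) | 1.25 | 0.4% | 19% | 82% |
| 52 (26) | 1.36 | 0.3% | 12% | 68% |
| 36 (18) | 1.73 | 0.09% | 3.4% | 29% |
| 30 (15) | 1.96 | 0.06% | 1.7% | 16% |

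The observed d needed is t(1 − 0.000005; df) × √(2/n). For n = 30 this is 4.84 × √(2/30) = 1.25.

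**Type I error.** If the interim p-value is valid and the final test is run at 0.05, as 9.8 and the synopsis say, the total is at most 0.05 + 0.00001 = 0.05001.

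**The case against.** The strongest reply is that the plan already covers this. Section 10.2 carries over methods and names no endpoint, and the wording in 9.8 could mean AUC over follow-up so far, with nothing imputed. Alternatively, the imputation rule in 9.9 reaches any missing endpoint data, and not yet due could be one of its reasons for missingness. That reason depends on enrolment date, so missing at random is comparatively plausible. The predictors listed need not be exhaustive, and the SAP or charter could hold the detail. Section 10.1 has the DSMC weigh whether enough information is available and lets it request more data. A very strict boundary attached to a safety meeting is a recognisable design choice, and properly done imputation widens the standard error, so the usual result is failure to stop.

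Much of this stands, and it limits the harm. It does not cure the mismatch. The text supports two different tests and does not choose between them. AUC so far would mix follow-up lengths, and a participant with only a Day 1 swab has no trapezoid: the AUC is zero and its log undefined. If nobody has reached Days 6-10, those values cannot be estimated from trial data. DSMC discretion governs the recommendation, not how the p-value is computed.

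A reader might infer that no AUC will be complete, because 10.2 says "We additionally expect blood count labs collected at day 5 to be available in approximately 25% of patients". If that figure tracks visits and review is at 1 day, it implies 10 to 15 enrolments per day and no complete AUC. It may instead reflect laboratory turnaround, and slower accrual leaves most AUCs complete, so the documents do not support that reading.

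**Conclusion.** The point holds as a mismatch between trigger and endpoint. A formal efficacy test is scheduled at 24 hours of follow-up, the tested hypothesis concerns AUC through Day 10, and no AUC has to be complete. This is true at any accrual rate, because everyone randomized in the nine days before the data cut is incomplete. Its extent depends on accrual, which is not stated: from about 7% incomplete at an assumed 0.5/day to everyone at 10/day with a 1-day review.

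Two stronger conclusions are tempting and should be resisted. One is that the look inflates type I error in a way that matters; with a valid interim p-value the excess is at most 0.00001. The other is that the plan has no interim population or missing-data rule; it has both, and only the treatment of swabs not yet due is unstated. At the planned d = 0.5 the boundary is almost uncrossable whatever the timing. Timing matters for a truly overwhelming effect, where at d = 1.5 the chance of stopping falls from 82% to 16% as complete AUCs fall from 60 to 30. The plan should be corrected, but this does not threaten the final analysis.

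**What to change.** **Preferred (a): make the 24-hour look safety-only.** Delete the p<0.00001 rule and the efficacy review in 10.2, the formal-efficacy sentence in 10.1, the interim alpha sentence in 9.2, and the mention of overwhelming efficacy in the synopsis. Reconcile the rest of 10.1, which still refers to "critical efficacy variables", to weighing safety and efficacy together, and to outcome data supplied to the DSMC. Test the primary endpoint at 0.05 throughout, replacing 0.04999 in 9.2. The cost is a look with about 0.4% power at d = 0.5, even with all 60 AUCs complete (19% at d = 1.0, 82% at d = 1.5). Final power at d = 0.5 stays at 77.5%, a change of about 0.003 percentage points.

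**Alternative (b): keep the 24-hour safety review and delay the efficacy test** until the first 60 randomized have passed Day 10 with nasal swabs assayed. Impute only swabs that were due and missed. State in 9.4 that the interim efficacy set is the first 60 randomized, as assigned; otherwise the restriction contradicts the ITT rule there. Give 0.04999 as the final alpha for the primary AUC test in 9.8 and the synopsis, to match 9.2.

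Option (b) is more than a wording change. It needs a second DSMC review and an interim swab assay, and power at d = 0.5 is still about 0.4%. The test falls due at day T + 9, when min(120, 60 + 9r) are enrolled before assay time: 69 at 1/day, 87 at 3/day and 105 at 5/day. All 120 are enrolled by then at 60/9 ≈ 6.7/day or faster, so it could not shorten enrolment.

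Section 9.1 can stand under either option. The SAP and DSMC charter should carry the same text.

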6.7 Clinically Significant Adverse Reactions

As indicated on the FOIPAN label (Japanese approved product), the below listed clinically significant adverse reactions may occur. Patients should be carefully monitored. If any abnormalities are observed, appropriate measures such as discontinuing the administration should be taken.

- Shock or anaphylactoid symptoms (both incidences unknown). If any symptoms such as decreased blood pressure, dyspnea, and pruritus are observed, administration should be discontinued and appropriate measures be taken.
- Thrombocytopenia (incidence unknown).
- Hepatic function disorder or jaundice (both incidences unknown).
- Hepatic function disorder accompanied by remarkable increase of AST (GOT), ALT (GPT), γ-GTP, Al-P, or jaundice may occur.
- Hyperkalemia (incidence unknown). Severe hyperkalemia may occur.

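### The safety data named for the only scheduled DSMC meeting with patient data contain no post-dose liver or potassium value and only partial platelet data

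*Combined protocol and SAP*

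**What the plan says.** Section 10.1 sets the meeting schedule: "The DSMC will meet before the study and during an interim analysis to review progress of the clinical trial and safety data". Only the second of these occasions can have patient data.

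Section 10.2 sets the trigger: "An interim analysis for safety and overwhelming efficacy will be performed once 50% of patients have 24 hours of follow-up complete". The meeting falls within a week of reaching half of enrolment, and its safety purpose is "to review the safety data collected within the first 24 hours of follow-up on all enrolled patients". One laboratory item is added: "We additionally expect blood count labs collected at day 5 to be available in approximately 25% of patients". The denominator of the 25% is not given. On efficacy the same section has no time window: "The DSMC will also review the efficacy data on all randomized participants at this meeting".

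Section 7.1 places the Day 1 hematology and chemistry draw before the first dose. Section 7.3 and the schedule in section 14 place the later draws on Days 5, 10 and 28. (The synopsis lists Days 1, 5 and 10 only; in either case the first post-dose draw is on Day 5.) Treatment runs for 10 days.

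Section 6.7 lists the clinically significant reactions on the product label. Besides shock or anaphylactoid symptoms, they are thrombocytopenia, hepatic function disorder or jaundice, and "Hyperkalemia (incidence unknown). Severe hyperkalemia may occur". The incidence of each is given as unknown.

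**The concern.** Three of the reactions in section 6.7 are found mainly through laboratory results. A window that closes 24 hours after entry, before any scheduled post-dose draw, cannot show them. The added Day 5 item is limited to blood counts. Liver enzymes, bilirubin and potassium are chemistry tests (section 8.3), and 10.2 does not mention chemistry, although section 14 takes CBC, Chem 7 and LFTs at the same Day 5 visit.

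What is at stake is the meaning of a recommendation to continue. In a double-blind trial, section 10.1 makes the DSMC the independent holder of comparative information. A between-arm shift in ALT or potassium that crosses no individual threshold and produces no SAE would be visible only in a comparison by arm. On the wording of 10.2, the scheduled meeting would not include that comparison, and no later meeting is scheduled that would.

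**Working it through.** **1. What the named package holds, by risk**

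| Risk in 6.7 | Test (8.3) | Scheduled post-dose value in first 24 h | Named Day 5 addition |
|---|---|---|---|
| Hepatic disorder or jaundice | AST, ALT, bilirubin, ALP (chemistry) | none | not named |
| Hyperkalemia | potassium (chemistry) | none | not named |
| Thrombocytopenia | platelet count (hematology) | none | blood counts, about 25% of patients |

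The gap is complete for liver and potassium and partial for platelets.

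**2. The plan's 25%**

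This figure cannot be reproduced, because no accrual rate is given. Its size depends on the denominator:

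- 25% of the 60 enrolled at the interim: 0.25 × 60 = 15 patients, 7 or 8 on camostat.
- 25% of the planned 120: 0.25 × 120 = 30 patients, 15 on camostat.

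As a range, assume uniform accrual at r patients per day and a data cut 1 day after the 60th patient. Day 5 is reached 4 days after entry, so a patient needs to have entered at least 3 days before the 60th. That leaves 60 − 3r patients with Day 5 reached, and likewise 60 − 8r with Day 10 reached.

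| Assumed r per day | Day 5 reached, of 60 | Day 10 reached, of 60 |
|---|---|---|
| 15 | 15 | 0 |
| 10 | 30 | 0 |
| 2 | 54 | 44 |
| 1 | 57 | 52 |

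A share of 25% of 60 thus implies about 15 patients a day with this cut. With slower accrual or a later cut, more Day 5 and Day 10 chemistry would already exist when the DSMC meets.

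**3. What numbers of this size can show**

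Inputs: n camostat patients with a post-dose value, and true event rate p. The three values of n are 8 (25% of 60, rounded up), 15 (25% of 120), and 30 (all camostat patients at the interim, 60/2).

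- Chance of at least one case: 1 − (1 − p)^n
- One-sided 95% upper bound on the rate when no case is seen: 1 − 0.05^(1/n)

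The documents give no rate for the reactions in 6.7, so p is assumed. 0.5% is the top of the 0.1%–0.5% band in section 6.8, where increased AST and ALT are listed. 5% is an illustrative higher value.

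| n | p = 0.5% | p = 1% | p = 5% | Upper bound, zero cases |
|---|---|---|---|---|
| 8 | 3.9% | 7.7% | 33.7% | 31% |
| 15 | 7.2% | 14.0% | 53.7% | 18% |
| 30 | 14.0% | 26.0% | 78.5% | 9.5% |

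Example: n = 8, p = 5% gives 1 − 0.95^8 = 0.337; n = 30, p = 0.5% gives 1 − 0.995^30 = 0.140.

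The rows for 8 and 15 apply to platelets under the stated package. For liver enzymes and potassium the package names no post-dose value, so n is 0. The row for 30 is what complete post-dose results on all interim patients would give.

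**The case against.** The strongest reply is that 10.2 should not be read alone. Section 10.1 says the DSMC assesses safety at intervals under a charter, lets it request additions once or on a continuing basis, and describes its package as including confidential outcome data and safety data with no time limit. The next sentence of 10.2 itself goes past 24 hours. The efficacy data at the same meeting cover all randomized participants, and the efficacy analyses in 9.9 include hospitalizations, respiratory failure and deaths. Outside the DSMC, SAEs reach the sponsor within 24 hours of the investigator's knowledge (8.3.6), the investigator and medical monitor follow AEs (8.3.3), removal criteria in 5.3 cover liver, platelet, creatinine and potassium findings, and the sponsor may stop the study at any time (13.1).

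Much of this stands, and it rules out several stronger readings. A reader might infer that the named risks go unreviewed by anyone, that only the DSMC could halt enrolment on safety, or that no later look is possible; the provisions just listed contradict all three. A reader might also infer that the DSMC decides on one tenth of the treatment period, or that weeks of Day 5 and Day 10 results are deliberately set aside. The first overlooks the Day 5 counts and the efficacy data. The second needs an accrual rate that the documents do not give, and chemistry is omitted from 10.2 rather than excluded.

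The objection does not remove the core. The power to request is optional and does not define the package. The charter is not among the documents. Patient-level rules act one patient at a time and do not compare arms. It is also fair to say that at rates near 0.5% even all 30 camostat patients would usually show nothing, so detection gains should not be oversold.

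**Conclusion.** The concern holds as a defect in the stated content of the DSMC safety review. As written, the safety data for the one scheduled meeting with patient data include no post-dose liver or potassium value, and platelet counts on about 15 patients (30 under the other denominator), of whom 7–8 (or 15) are on camostat. No comparative DSMC review of Day 5 chemistry, or of Day 10 or Day 28 laboratory results, is scheduled.

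The practical size is uncertain. For platelets, going from 8 to 30 camostat patients raises the chance of seeing a case from about 34% to 79% if the true rate is 5%, but only from about 4% to 14% if it is 0.5%. These figures rest on assumed rates, equal allocation at the interim, and results being available on every interim patient in the row for 30. Whether one data meeting is enough for a 120-patient, 10-day treatment trial is a matter of judgement; the content of that meeting is the firmer point. It should be corrected, because the change is specific and nearly free.

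**What to change.** In section 10.2, replace the safety-data phrase quoted above with: *all safety data accumulated to the data cut on every dosed patient, by arm, including AEs, SAEs and all available post-dose hematology and chemistry (AST, ALT, bilirubin, potassium, creatinine, platelets)*. State the denominator of the 25% in the same paragraph, and carry the wording into the DSMC charter.

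Cost: a protocol and charter wording change and a slightly larger DSMC report. The samples are already scheduled, so no patient, visit or procedure is added and no clinical threshold changes.

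Optional, for the sponsor and DSMC to judge: circulate one further safety report to the DSMC once the first 60 patients have Day 10 laboratory results. Its value depends on accrual. At 15 patients a day the second 60 would enrol in 60/15 = 4 days, so the report would arrive after enrolment had closed; at 1–2 a day it would arrive while patients were still being enrolled.
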